11.3. Efficacy Analysis

ORR is the primary efficacy endpoint. For solid tumors, response evaluation will be based on the RECIST criteria (v1.1) and ORR is defined as the proportion of subjects with complete response (CR) or partial response (PR) on two consecutive tumor assessments at least 4 weeks apart according to RECIST (RECIST v1.1). In addition, immune-related RECIST (irRECIST) criteria will also be used for Probody therapeutics that are likely to be immunostimulating. For lymphoma, objective response will be based on tumor-specific criteria.

The secondary efficacy endpoints include duration of response (DOR), TTR, progression-free survival (PFS), and overall survival (OS).

TTR is defined as the time from the date of the first dose of study drug to first documentation of objective tumor response. TTR is only calculated for subjects in the response-evaluable population who have a confirmed objective tumor response.

DOR is defined as the time from the first documentation of objective tumor response that is subsequently confirmed to the first documentation of objective disease progression or death due to any cause, whichever occurred first. DOR is only calculated for subjects in the response-evaluable population who have a confirmed objective tumor response. Subjects who neither progress nor die will be censored on the date of their last tumor assessment.

PFS is defined as the time from the date of the first dose of study drug to the date of first documentation of objective tumor progression or death due to any cause, whichever occurs first. Subjects who die without a reported progression will be considered to have progressed on the date of their death. Subjects who did not progress or die will be censored on the date of their last tumor assessment. Subjects who did not have any on-study tumor assessments and did not die will be censored on their date of enrollment/randomization (as applicable). Subjects who started anti-cancer therapy without a prior reported progression will be censored on the date of their last tumor assessment prior to the initiation of subsequent anti-cancer therapy.

OS is defined as the time from the date of the first dose of study drug to the date of death due to any cause. All deaths will be included in the analysis.

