5.1.2 Primary Efficacy Endpoint

The primary criteria for defining evidence of anti-cancer activity and also for management of subject care will be a clinical response as defined by RECIST (Version 1.1). ORR is the primary efficacy endpoint and ORR is defined as the proportion of subjects with complete response (CR) or partial response (PR) on two consecutive tumor assessments at least 4 weeks apart according to RECIST (RECIST v1.1).

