13.1.1 Primary Efficacy Endpoint

The ORR is the primary efficacy endpoint. For solid tumors, response evaluation will be based on the RECIST criteria (v1.1) and ORR is defined as the proportion of subjects with complete response (CR) or partial response (PR) on two consecutive tumor assessments with scan dates at least 4 weeks apart according to RECIST (RECIST v1.1).

The primary efficacy analysis will be based on the REP. Exact 2-sided 95% Cis (using the Clopper-Pearson method) will be calculated for all proportion estimates.

A listing of tumor data including total tumor burden, RECIST v1.1 response assessments (target lesion evaluation, non-target lesion evaluation, and overall subject response) will be provided.

Response Assessment and Best Overall Response – RECIST v1.1

Efficacy outcomes will be summarized by dose level and by cancer type using RECIST v1.1 among the REP. The overall number of subjects for each dose; and the number, proportion, and 95% exact 2-sided CI (using the Clopper-Pearson method) of confirmed CR and PR, unconfirmed CR and PR, SD, PD, not evaluable (NE), overall response (CR + PR), disease control (CR + PR + SD) will be calculated. A summary table of the above response assessments by part using RECIST v1.1 among the REP will be provided. A swim lane plot of response assessment status over time using RECIST v1.1 will be produced.

The best overall response is the best response recorded from the start of study treatment until the end of treatment taking into account any requirement for confirmation. If the best overall response is determined before the end of treatment (e.g., for an interim data cut), then it is the best response recorded from the start of study treatment until the date of the data cut.

When no imaging/measurement is done at all at a particular time point, the subject is not evaluable (NE) at that time point. If only a subset of lesion measurements are made at an assessment, usually the case is also considered NE at that time point, unless a convincing argument can be made that the contribution of the individual missing lesion(s) would not change the assigned time point response (as may happen in the case of an assessment of PD).

Complete or partial responses may be claimed only if the criteria for each are met at a subsequent time point as specified in the protocol (i.e., ~8 weeks later and no

earlier than 4 weeks later). In this circumstance, the best overall response can be interpreted as in Table 1.

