In the case of SD, measurements must have met the SD criteria at least once after study entry at a minimum interval of 7 weeks. If the first post-baseline response assessment is an SD and the assessment was less than 7 weeks from first dose of study drug, then the SD would be changed to NE. For the dose escalation parts of the study (i.e., parts A, A2), the reporting of CR/PR does not require confirmation as the primary objective is safety. Confirmation is required for the expansion cohorts (i.e., Part B).

Table 1: Best Overall Response Algorithm

| Overall Response First Time Point | Overall Response Subsequent Time Point | Best Overall Response |
|-----------------------------------|--|---|
| CR | CR | CR |
| CR | PR | SD, PD, or PR ^a |
| CR | SD | SD provided minimum criteria for SD duration met, otherwise, PD |
| CR | PD | SD provided minimum criteria for SD duration met, otherwise, PD |
| CR | NE | SD provided minimum criteria for SD duration met, otherwise, NE |
| PR | CR | PR |
| PR | PR | PR |
| PR | SD | SD |
| PR | PD | SD provided minimum criteria for SD duration met, otherwise, PD |
| PR | NE | SD provided minimum criteria for SD duration met, otherwise, NE |
| NE | NE | NE |

CR = complete response, PR = partial response, SD = stable disease, PD = progressive disease, and NE = not evaluable.

^a If a CR is truly met at first time point, then any disease seen at a subsequent time point, even disease meeting PR criteria relative to baseline makes the disease PD at that point (since disease must have reappeared after CR). Best response would depend on whether minimum duration for SD was met. However, sometimes 'CR' may be claimed when subsequent scans suggest small lesions were likely still present and in fact the subject had PR, not CR at the first time point. Under these circumstances, the original CR should be changed to PR and the best response is PR.

Tumor burden assessed using RECIST v1.1 will be calculated as the sum of (the longest diameter of target non-nodal lesions plus the short axis of target nodal lesions). The percent change from baseline will be plotted by time on study as a spider plot. The maximum percent change from baseline will be plotted in a waterfall plot. The spider and waterfall plots will include all visits regardless of whether or not a response assessment has been recorded (as long as all baseline target lesions were measured at the visit).

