13.1.2 Secondary Efficacy Endpoints

Secondary efficacy endpoints are:

- DOR,
- TTR,
- PFS, and
- OS.

Time-to-Event Endpoints

DOR

DOR is defined as the time from the date of the first documentation of objective tumor response (i.e., ORR = CR or PR) that is subsequently confirmed to the date of the first documentation of objective disease progression or death due to any cause, whichever occurred first. DOR is only calculated for subjects in the REP who have a confirmed objective tumor response. Subjects who neither progress nor die will be censored on the date of their last tumor assessment.

Table 2 Date of Censoring – DOR

| Description of Situation | Date of Progression or Censoring | Outcome |
|---|---|----------------|
| No disease progression nor death on-study | Date of last tumor assessment | Censored |

TTR

TTR is defined as the time from the date of the first dose of study drug to first documentation of confirmed objective tumor response. TTR is only calculated for subjects in the REP.

PFS

PFS is defined as the time from the date of the first dose of study drug to the date of first documentation of objective tumor progression (i.e., PD) or death due to any cause, whichever occurs first. Subjects who die without a reported progression will be considered to have progressed on the date of their death. Subjects who did not progress or die will be censored on the date of their last tumor assessment. Subjects who did not have any on-study tumor assessments and did not die will be censored on their date of first dose of study treatment. Subjects who started anti-cancer therapy without a prior reported progression will be censored on the date of their last tumor assessment prior to the initiation of subsequent anti-cancer therapy. PFS is calculated for using the SP.

Table 3. Date of Progression or Censoring -- PFS

| Description of Situation | Date of Progression or Censoring | Outcome |
|---------------------------------|---|----------------|
| No baseline disease assessments | Date of first dose of study drug | Censored |

| | | |
|---|---|------------|
| Death before first disease assessment | Date of death | Progressed |
| No disease progression nor death on-study | Date of last tumor assessment with a response assessment other than not evaluable | Censored |
| Death without a reported progression | Date of death | Progressed |
| No on-study tumor assessments and did not die | Date of first dose of study drug | Censored |

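### SAP 13.1.1 waives confirmation of CR/PR in Parts A and A2 although ORR is defined as confirmed for every part, and the overall response row does not say which rule it uses

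*SAP*

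**What the plan says.** SAP 5.1.2 builds the ORR numerator from subjects showing "complete response (CR) or partial response (PR) on two consecutive tumor assessments at least 4 weeks apart according to RECIST". SAP 13.1.1 repeats this: "ORR is defined as the proportion of subjects with complete response (CR) or partial response (PR) on two consecutive tumor assessments". It too asks for a gap of no less than 4 weeks between the two scans. Neither section excepts a study part. The Core (Protocol Appendix A, section 11.3) has the same definition: "partial response (PR) on two consecutive tumor assessments at least 4 weeks apart according to RECIST".

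SAP 13.1.1 then sets a general rule: "Complete or partial responses may be claimed only if the criteria for each are met at a subsequent time point". Its Table 1 converts pairs of assessments into a best overall response with confirmation built in; for example, a PR followed by SD is classed as SD. Best overall response is to be derived "taking into account any requirement for confirmation".

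Just before Table 1 comes the waiver. For the dose escalation parts, identified as A and A2, "the reporting of CR/PR does not require confirmation as the primary objective is safety". The next sentence requires confirmation for the expansion cohorts, identified as Part B. Part C1 appears in neither sentence, although SAP 4.1 describes it as dose escalation.

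The planned response table lists confirmed CR and PR and then "unconfirmed CR and PR, SD, PD, not evaluable (NE), overall response (CR + PR), disease control". The overall response row carries no qualifier. In SAP 13.1.2, "DOR is only calculated for subjects in the REP who have a confirmed objective tumor response", and TTR also runs to a confirmed response.

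**The concern.** One section gives two rules for the same subjects, and the row a reader will take as the ORR names neither. If the waiver is applied to that row in Parts A and A2:

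- The printed ORR departs from its definition in SAP 5.1.2 and 13.1.1.
- The ORR numerator includes responders whom DOR and TTR exclude.
- The dose tables pool Parts A, A2 and B (SAP 10.1), so the 7 mg/kg row can add unconfirmed A/A2 responses to confirmed Part B responses.
- CBR16 and CBR24, which count a best overall response of CR or PR whatever its duration (SAP 13.1.2), can change.

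The precedence clause in Protocol 9.2 ranks the SAP above the Core, so it cannot resolve a conflict inside the SAP. SAP section 1 says the outputs will support publications and FDA submissions, where the choice of rate would matter.

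**Working it through.** **Inputs**
- Treated subjects (SAP 4.2): 37 in Part A, 10 in the mTPI-2 cohort, 39 in Part A2, 3 in Part B, 10 in Part C1. SAP 4.1 treats the mTPI-2 cohort as the final stage of Part A.
- Responses at 30 November 2019 (Protocol 1.3.4.2): 2 confirmed PRs and 6 unconfirmed PRs among 92 subjects.
- Schedule (Protocol 1.3.4.1): all but 6 of the 92 were dosed every 21 days.
- Interval method (SAP 13.1.1): exact two-sided 95% Clopper-Pearson. For x responders of n, the lower limit is the 2.5% quantile of Beta(x, n − x + 1) and the upper limit is the 97.5% quantile of Beta(x + 1, n − x).

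**Protocol figures reproduced.** 2/92 = 2.17% and 6/92 = 6.52%, matching the stated 2.2% and 6.5%.

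**Share of subjects under the waiver.** 37 + 10 + 39 = 86, and 86/99 = 87%.

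**Both rules on the same 92 subjects**, taking the confirmed and unconfirmed PRs as different people:

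| Rule | Responders | Rate | Exact 95% CI |
|---|---|---|---|
| Confirmed only | 2/92 | 2.2% | 0.3–7.6% |
| Unconfirmed included | 2 + 6 = 8/92 | 8.7% | 3.8–16.4% |

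The rates differ fourfold (8 against 2).

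**Every-21-day subjects only.** 92 − 6 = 86, which agrees with 47 in Part A plus 39 in Part A2 (Protocol 3.2 and 3.4). The split of responders by schedule is not given. With u unconfirmed PRs among the 86, the gap is u/86, and u cannot exceed 6. The gap is therefore at most 6/86 = 7.0 points. If all eight responders were on this schedule, the two rates would be 2/86 = 2.3% (0.3–8.2%) and 8/86 = 9.3% (4.1–17.5%).

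**Pooled 7 mg/kg row.** Protocol 1.3.4.1 gives 9 subjects at 7 mg/kg every 21 days, and Part B adds 3, assuming they were dosed at 7 mg/kg as planned and all are evaluable. The row then has 12 subjects, and each unconfirmed A/A2 response counted moves it by 1/12 = 8.3 points. The documents do not say whether any occurred at that dose.

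**CBR, by example.** Take a PR at week 8 and PD at week 15, which the 8 (±1) week scan schedule allows. Under the waiver the best response is PR, so the subject counts in CBR16 and CBR24. Under Table 1 it is SD lasting 15 weeks, so the subject counts in neither.

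**Disease control.** Little change is expected. An unconfirmed PR generally becomes SD under Table 1, and the 7-week minimum for SD coincides with the earliest scheduled first scan (8 − 1 weeks).

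**The case against.** The strongest reply is that the text can be read as consistent. Best overall response defers to whatever confirmation requirement applies, and the waiver then states that requirement by part and gives a reason. It speaks of reporting CR/PR and does not mention ORR, so ORR could remain confirmed throughout, which would fit DOR and TTR. Confirmed and unconfirmed rows, each with an exact interval, and a by-part table are already planned, so both rates will be visible. ORR in Parts A, A2 and C1 is a secondary, preliminary measure.

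Much of this stands. It limits the harm, and it means that conflicting outputs are possible rather than certain. It does not label the CR + PR row, and no unconfirmed algorithm accompanies the waiver. If the consistent reading is what was meant, writing it down is exactly the fix proposed.

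Outside support is modest. The SAP outranks the Core. The supplied Module requires confirmation in Parts A, A2 and B (Appendix B, Table 13, note 6) and in C1 (Table 14, note 6), but the SAP cites Module Amendment 06 of August 2017, while the supplied Module carries November 2019 data. The Module itself uses ORR both ways: section 5.2.1.2 reports about 8% of 38 subjects, all unconfirmed, which is 0/38 under the SAP definition, while section 9 relies on a confirmed ORR when dropping Part B's two-stage design. That shows the ambiguity matters in practice, but it does not favour either rule.

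**Conclusion.** The conflict is real, lies within the SAP and should be fixed. On the interim counts it is the difference between 2.2% and 8.7% in 92 subjects, and at most 7.0 points in the 86 every-21-day subjects. These figures are illustrative: the 92 may not match the SAP's response-evaluable population, which requires a post-baseline assessment, and some unconfirmed PRs may have been awaiting a confirmatory scan.

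Four stronger readings are not supported:

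- **That Part C1 is confirmed by default.** The SAP lists C1 under neither rule, and the waiver's stated reason, a safety primary objective, would fit C1 as well. Its rule is simply unclear.
- **That the gap has a known minimum.** A reader might take 3 unconfirmed PRs from the approximate 8% of 38 at the 28 October 2019 cut, subtract the 2 confirmed by 30 November, and conclude that at least 1/86 = 1.2 points must remain. That mixes two data cuts and infers a count from a rounded percentage, so no minimum is given here.
- **That the waiver must be removed altogether.** Confining it to the unconfirmed row cures the conflict equally well.
- **That Part B's primary result is affected.** Confirmation is explicitly required there.

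**What to change.** In SAP 13.1.1, state that ORR, the overall response (CR + PR) row, and the best overall response used for disease control and CBR16/CBR24 all use confirmed CR/PR under Table 1 in Parts A (including the mTPI-2 cohort), A2, B and C1. Then either delete the waiver sentence or limit it to the already planned unconfirmed CR/PR row, labelled as supportive and not added to ORR. An unconfirmed responder then enters disease control or CBR only if Table 1 classes that subject as SD and, for CBR, the SD duration is met.

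The cost is one sentence added and one removed or narrowed, with no new table or row. The drawback is that the ORR reported for the escalation parts may look less favourable.

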13.1.2 Secondary Efficacy Endpoints

Secondary efficacy endpoints are:

- DOR,
- TTR,
- PFS, and
- OS.

Time-to-Event Endpoints

DOR

DOR is defined as the time from the date of the first documentation of objective tumor response (i.e., ORR = CR or PR) that is subsequently confirmed to the date of the first documentation of objective disease progression or death due to any cause, whichever occurred first. DOR is only calculated for subjects in the REP who have a confirmed objective tumor response. Subjects who neither progress nor die will be censored on the date of their last tumor assessment.

Table 2 Date of Censoring – DOR

| Description of Situation | Date of Progression or Censoring | Outcome |
|---|---|----------------|
| No disease progression nor death on-study | Date of last tumor assessment | Censored |

TTR

TTR is defined as the time from the date of the first dose of study drug to first documentation of confirmed objective tumor response. TTR is only calculated for subjects in the REP.

PFS

PFS is defined as the time from the date of the first dose of study drug to the date of first documentation of objective tumor progression (i.e., PD) or death due to any cause, whichever occurs first. Subjects who die without a reported progression will be considered to have progressed on the date of their death. Subjects who did not progress or die will be censored on the date of their last tumor assessment. Subjects who did not have any on-study tumor assessments and did not die will be censored on their date of first dose of study treatment. Subjects who started anti-cancer therapy without a prior reported progression will be censored on the date of their last tumor assessment prior to the initiation of subsequent anti-cancer therapy. PFS is calculated for using the SP.

Table 3. Date of Progression or Censoring -- PFS

| Description of Situation | Date of Progression or Censoring | Outcome |
|---------------------------------|---|----------------|
| No baseline disease assessments | Date of first dose of study drug | Censored |

| | | |
|---|---|------------|
| Death before first disease assessment | Date of death | Progressed |
| No disease progression nor death on-study | Date of last tumor assessment with a response assessment other than not evaluable | Censored |
| Death without a reported progression | Date of death | Progressed |
| No on-study tumor assessments and did not die | Date of first dose of study drug | Censored |
| Subjects who started anti-cancer therapy without a prior reported progression | Date of their last tumor assessment with a response assessment other than not evaluable prior to the initiation of subsequent anti-cancer therapy | Censored |
| Died or progressed (on treatment*) after a missed assessment | Date of death or disease progression | Progressed |
| Died or progressed in follow-up | Date of last tumor assessment with a response assessment other than not evaluable | Censored |

* Subjects who discontinued the study 30 or fewer days from the last dose of study drug are considered to have discontinued the study during the treatment period. Subjects who discontinue the study more than 30 days after the last dose of study drug are considered to have discontinued the study while in follow-up.

OS

OS is defined as the time from the date of the first dose of study drug to the date of death due to any cause (as captured on the Study Discontinuation, Treatment Termination, Substudy Discontinuation, Survival Status and/or AE CRF pages). Two analyses of OS will be conducted. The first will analyze all on-treatment deaths (deaths occurring within 30 days of last dose of study drug) while the second will analyze all on-study deaths (deaths occurring after first dose of study drug while on study). Subjects who are last known to be alive and/or lost to follow-up are censored at the date of last contact (as captured on the Discontinuation Call, Study Discontinuation, Treatment Termination, Survival Status, and/or Substudy Discontinuation CRF pages). Interim analyses of OS would use the data cut date as the censoring date of last contact if the subject is last known to be alive and/or lost to follow-up. OS is calculated for using the SP.

Table 4. Date of Censoring

| Description of Situation | Date of Progression or Censoring | Outcome |
|---|----------------------------------|----------|
| Last known to be alive and/or lost to follow-up | Date of last contact | Censored |

Please note that the scan date of the tumor assessment associated with the reported response assessment will be used as the tumor response date referenced above (i.e., first documentation of objective tumor response, first documentation of objective disease progression, and first documentation of objective tumor progression).

Estimates of time-to-event endpoints (DOR, TTR, PFS, and OS) will be obtained using the Kaplan-Meier method. Kaplan-Meier curves will be provided for these endpoints. A swim lane plot will be provided for DOR. DOR and TTR will also be summarized using descriptive statistics for confirmed objective responders.

The median, and 95% CIs around the DOR, TTR, PFS, and OS will also be calculated using the Kaplan-Meier method. The range of TTR, PFS and OS will be provided as well. Frequencies and percentages will be summarized for event rates and censored observations of the time-to-event endpoints. Six- and twelve-month and 2-year survival rates will be included as well. The number and percentage of disease progressions and deaths will be included (replacing the event rate) in the PFS summary.

CBR16 and CBR24

Breast cancer patients will also have CBR16 and CBR24 summarized by dose level and also by cancer subtype (TNBC, HR+/HER2-, HER2+). CBR16 is defined as the proportion of subjects with best overall response of CR or PR or with SD for at least 16 weeks. CBR24 is defined as the proportion of subjects with best overall response of CR or PR or with SD for at least 24 weeks. CBR16 and CBR24 will only be calculated for subjects in the REP.

SD Duration is defined as the time interval from the start of the treatment to the date of subsequent PD or on-treatment death. In the absence of PD or on-treatment death before the analysis cut-off date, it is the time from the start of treatment to the date of the last adequate tumor assessment before the cut-off date.

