4.3 Study Periods and Follow-Up

The study is divided into periods with associated evaluations and procedures that must be performed at specific time points. The schedule of procedures in Appendix B of the CTMX-M-2009-001 Protocol Module summarizes the frequency and timing of efficacy, safety, and other study measurements. Refer to the Common Core Document for a description of each procedure.

As with any Phase 1 study, an individual subject's participation in the study is difficult to predict. It is estimated that average treatment will last approximately 6 months, followed by Follow-Up contact every 3 to 6 months for another 1 to 2 years, or as long as the subject remains alive (Figure 3).

Figure 3: Study Periods

Notes: An EOT Visit will be conducted 30 days (± 7 days) after the last infusion of study treatment. Follow-Up: If subject has not had progression, imaging assessments will continue until progression is documented. If subject had documented progression, the subject will continue in survival Follow-Up Visits every 3 months (± 14 days) after the EOT Visit for 1 year and then every 6 months (± 14 days) (this may be by telephone), or until death. Subsequent cancer treatment will be collected. Survival Follow-Up will be done every 3 months (± 14 days) as described above.

DLT = dose-limiting toxicity; EOT = end of treatment; IV = intravenous; q14 = every 14; q21 = every 21.

Following the completion of study treatment, subjects with progressive disease per RECIST v1.1 as measured by investigator assessment, will return for an end of treatment (EOT) Visit and then enter the Follow-Up Period for monitoring of survival. Subjects who for other reasons stop study drug treatment and subjects with stable disease, confirmed partial response, or confirmed complete response will enter the Follow-Up Period for monitoring of DOR and PFS.

The study will be completed approximately 2 years from the date the last subject is enrolled or when the last subject has completed treatment and the last Follow-Up Visit.

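### SD Duration (hence the stable-disease part of CBR16/CBR24) and DOR have no stop at new anti-cancer therapy, although PFS does

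*SAP*

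**What the plan says.** The rules in SAP 13.1.2 differ by endpoint.

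- **PFS.** "Subjects who started anti-cancer therapy without a prior reported progression will be censored on the date of their last tumor assessment prior to" the start of that therapy. Table 3 repeats this as a row and limits it to evaluable assessments. Another Table 3 row, "Died or progressed in follow-up", is also censored at the last evaluable assessment.
- **DOR.** "Subjects who neither progress nor die will be censored on the date of their last tumor assessment". Table 2 has a single row: "No disease progression nor death on-study | Date of last tumor assessment | Censored". Core 11.3 gives DOR the same rule and, like the SAP, states a new-therapy rule only for PFS. It also says that "DOR is only calculated for subjects in the response-evaluable population who have a confirmed objective tumor response".
- **SD Duration.** It starts with treatment and ends at progression or at a death on treatment. For subjects with neither, the SAP says "In the absence of PD or on-treatment death before the analysis cut-off date, it is the time from the start of treatment". The end point is then the latest adequate scan before the data cut. Adequate is not defined.
- **CBR16 and CBR24.** These are summarised for breast cancer subjects in the response-evaluable population. A subject qualifies with a best overall response of CR or PR, or with SD lasting at least 16 or 24 weeks. SAP 13.1.1 limits best overall response to the period up to end of treatment.

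On conduct, SAP 4.3 says "If subject has not had progression, imaging assessments will continue until progression is documented", and later cancer treatment is recorded. SAP 4.5 lists the need for other anti-cancer treatment as a reason to stop study drug, separately from progression.

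**The concern.** Scanning continues after CX-2009 stops without progression, and nothing ends it when another drug starts. Scans taken on the next treatment can therefore enter both SD Duration and DOR. PFS in the same section is protected from this, and the SAP gives no reason for treating the measures differently.

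At stake is what CBR16 and CBR24 mean. They would be read as disease control by CX-2009, yet stability maintained by another drug can satisfy them. For DOR, a responder's recorded duration can include time on another therapy and can run past the date at which that subject's PFS was censored. The SAP is meant to support publications and FDA submissions (SAP 1), so an undeclared difference in rules between related endpoints should be settled before reporting.

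**Working it through.** The plan states no rate, median or sample size for DOR, CBR16 or CBR24, so there is no figure to reproduce. The check applies the written rules to hypothetical subjects. Scans fall every 8 (±1) weeks (Protocol Appendix B, Table 13).

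**SD Duration and CBR.** Assume SD at week 8, CX-2009 stopped without PD, new therapy at week 10, and scans at weeks 16 and 24.

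- As written, with SD at week 16 and SD or PD at week 24: duration is 24 weeks. The subject counts in CBR16 and CBR24.
- As written, with PD at week 16: duration is 16 weeks. The subject counts in CBR16.
- With a stop at new therapy: duration is 8 weeks. An extra scan before week 10 could raise it to at most 10 weeks. The subject counts in neither.

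The stop only removes later follow-up, so duration as written is never shorter than with the stop, and the bias in CBR can only be upward. Each affected subject adds 1/n: 1/20 = 5.0 points at an assumed n = 20, and 1/40 = 2.5 points at n = 40.

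**One responder's DOR.** Assume PR at week 8, confirmed at week 16, and CX-2009 stopped at week 17 on undelayed 21-day dosing, so the last infusion was at week 15. Non-progressors are scanned at the EOT visit, 30 ±7 days after the last infusion (Table 13, footnotes 6 and 24). That is week 15 + 23/7 = 18.3 to week 15 + 37/7 = 20.3, centred on 15 + 30/7 = 19.3. Assume the EOT scan is at 19.3 without PD, new therapy starts at week 20, and PD is seen at the week-48 scan.

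- PFS: censored at week 19.3.
- DOR as written: an event at 48 − 8 = 40 weeks, of which 48 − 20 = 28 weeks follow the start of the next therapy.
- DOR with the Table 3 new-therapy row: censored at 19.3 − 8 = 11.3 weeks.

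Now suppose this subject takes no other therapy and progresses at week 48. That is 48 − 15 = 33 weeks after the last infusion, hence in follow-up. Table 3 censors PFS, while DOR is still an event at 40 weeks. A new-therapy row alone therefore does not reconcile the two endpoints.

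**Kaplan-Meier DOR across responders.** Assume 8 responders. Five do not switch: events at weeks 8, 16, 16 and 24, and one censored at 32. Three switch therapy, each with a last pre-switch scan at week 8. The median is the first time at which the curve is at or below 0.5.

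- Switchers censored at week 8: S(8) = 7/8 = 0.875; S(16) = 0.875 × 2/4 = 0.438. Median 16 weeks.
- As written, switchers late (events at 40 and 48, one censored at 48): S(16) = 0.875 × 5/7 = 0.625; S(24) = 0.625 × 4/5 = 0.500. Median 24 weeks.
- As written, all three switchers progress at week 16: S(16) = 0.875 × 2/7 = 0.250. Median stays at 16 weeks, but the curve is lower than 0.438.

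The median itself can also fall. Move the two non-switchers' week-16 events to week 24. With switchers censored at week 8, S(24) = 0.875 × 1/4 = 0.219 and the median is 24 weeks. As written, with the switchers progressing at week 16, S(16) = 0.875 × 4/7 = 0.500 and the median is 16 weeks.

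**The case against.** The strongest reply has four parts.

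First, following DOR regardless of later therapy is a recognised treatment-policy choice. Both documents monitor DOR after study drug stops, and censoring at new therapy can itself be informative. This stands as an option, but neither document declares it.

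Second, adequate might be read as excluding scans on another drug. The text does not say so, and where the SAP wants a pre-therapy restriction, as for PFS, it writes one.

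Third, the practical weight is limited. Enrolment stopped at 99 treated subjects, 3 of them in Part B (SAP 4.2). Two of 92 subjects had a confirmed PR at the November 2019 data lock (Protocol 1.3.4.2). CBR16 and CBR24 are descriptive, confined to breast cancer and absent from the listed secondary endpoints. SAP 1 allows analyses to be dropped if numbers are too small. All of this stands and limits the importance of the point.

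Fourth, the documents do not count subjects who switch without progression and are scanned afterwards. This also stands. A reader might infer from the ocular toxicity and neuropathy rates in Protocol 1.3.4.1 that such subjects are common, or that poor tolerability improves these endpoints. Those rates show only that stopping without progression is plausible. They do not show how often it is followed by new therapy and further scans.

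**Conclusion.** The gap is real. Neither SD Duration nor DOR stops at new anti-cancer therapy, PFS does, and the Core does not supply the missing rule.

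The consequence is firmest for CBR16 and CBR24: the bias can only be upward, by 1/n per affected subject (5 points at an assumed n = 20). A reader might infer that the whole of CBR is exposed. It is not, because a CR or PR must be reached by end of treatment.

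For DOR, an affected responder's own duration can only lengthen, which matters for the planned descriptive summary of responders. A reader might infer that the Kaplan-Meier median is therefore inflated. The rules do not support that: PD and death on the next therapy also become events, so the estimate can move either way. Nor does a DOR event time longer than the same subject's PFS censoring time mean that DOR truly exceeds PFS, since the PFS time is censored. It means that the two rules follow the subject for different lengths of time, partly because of the Table 3 row on events in follow-up.

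The overall size is unknown. The timelines are hypothetical, and the group sizes of 20 and 40 are assumptions.

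**What to change.** 1. **SD Duration.** State that, absent earlier PD or on-treatment death, it ends at the last adequate tumor assessment before subsequent anti-cancer therapy starts (or before the data cut, if there is none).
2. **DOR.** Add to Table 2 the row that Table 3 already has: censoring at the last evaluable assessment before subsequent anti-cancer therapy. If DOR regardless of later therapy is intended, say so and report the censored version as a sensitivity analysis.
3. **Follow-up events.** Make DOR and PFS consistent on progression or death in follow-up, since the new-therapy row alone leaves that conflict in place.

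The cost is a few SAP sentences and a table row. Subsequent treatment is already collected, and the PFS rule needs the same programming. CBR may come out slightly lower, and DOR may have more censoring.
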